## **9.3 Clinical Laboratory Data**

For clinical laboratory tests other than qualitative urinalysis (except for pH and specific gravity in urinalysis), descriptive statistics of the measured values and changes from baseline at each time point after the start of administration at the evaluation dose and on the day after the final administration will be calculated. For qualitative urinalysis parameters, shift tables at each time point after the start of administration at the evaluation dose and on the day after the final administration compared with baseline will be prepared (except for color). For clinical laboratory test parameters other than qualitative urinalysis, a specified site reference range will be used to classify the measurements into measurements “within the reference range,” “below the reference range,” or “above the reference range,” and shift tables of classifications at each time point after the start of administration at the evaluation dose and on the day after the final administration compared with baseline will be prepared.

An analysis will also be performed using data collected immediately before start of administration at evaluation dose as a baseline. In addition, data will be summarized by the number of days elapsed since start of administration.

For ALP, the value calculated by the IFCC method will be used for the descriptive statistics (for the measured values by the JSCC method, a conversion factor of 0.35 will be used to summarize the converted values).

#### **9.4 Vital Sign Data**

For vital signs, descriptive statistics of measured values and changes from baseline at each time point after the start of administration at the evaluation dose and on the day after the final administration will be calculated.

An analysis will also be performed using data collected immediately before start of administration at evaluation dose as a baseline. In addition, data will be summarized by the number of days elapsed since start of administration.

#### **9.5 Electrocardiogram Data**

For each 12-lead ECG parameter, descriptive statistics of measured values and changes from baseline will be calculated on the day after the final administration and the follow-up period.

For QTc interval (QTcB, QTcF), the number and percentage of subjects with a QTc interval of > 450, > 480, or > 500 msec measured at baseline, on the day after the final administration and in the follow-up period will be calculated. The number and percentage of subjects with a change in QTc interval from baseline of > 30 or > 60 msec on the day after the final administration and the follow-up period will also be calculated. A shift table for QTc interpretation (normal or abnormal) will be prepared from baseline through the day after the final administration and follow-up period. The QTc interpretation (normal or abnormal) by the site (the investigator or subinvestigator) will be used rather than that of the central ECG measurement facility.

### **10 Pharmacokinetic Analyses**

In the pharmacokinetic analysis set, the plasma concentrations of OPC-41061 and its metabolites (DM-4103 and DM-4107) will be summarized by descriptive statistics, in the following 2 ways. The doses used for tabulation (0.05, 0.15, 0.3, and 0.5 mg/kg/day) will be those on the date of blood sampling (the classification entered in the CRF).

- Summarization for each compound, time point of blood sampling, and dose
- Summarization for each compound, time point of blood sampling, dose, and age group (young age, 6 months to less than 2 years; middle age, 2 years to less than 7 years; and old age, 7 years to less than 15 years)

Descriptive statistics to be determined are the number of subjects, mean, standard deviation, coefficient of variation, minimum, median, and maximum.

For OPC-41061, a figure of changes in the plasma concentration will also be prepared for each subject by dose. The actual time points of blood sampling (“0 (zero)” before administration) will be used for the horizontal axis (X axis) of the figure.

When calculating descriptive statistics and preparing figures, plasma drug concentrations below the lower limit of quantitation will be handled as “0 (zero)” until the first quantitative value after administration is obtained and as missing values after the quantitative value.

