3.7.1.3.10 Day After Final Administration

If administration at the dose decided for each individual subject is completed in 3 days, the investigator or subinvestigator will perform the following procedures on the day after final administration.

1) Before breakfast

- Body weight
- Laboratory tests
- Serum or blood sodium concentration
- Serum or blood potassium concentration
- Serum osmolality
- Plasma AVP concentration (only subjects from whom samples are available)

- Plasma drug concentration: Assessment after breakfast is allowed.
- 2) At a feasible time
 - Vital signs
 - 12-lead ECG
 - Edematous symptoms
 - Chest x-ray
 - Concomitant drugs and therapies
 - Adverse events

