3.7.1.5.1 First Day of Administration at Reduced Dose

The investigator or subinvestigator will perform the following procedures.

1) Before tolvaptan administration

The investigator or subinvestigator will perform the following examinations, and then, offer breakfast to the subject.

- Body weight
- Laboratory tests
- Serum or blood sodium concentration
- Serum or blood potassium concentration
- Serum osmolality
- Plasma AVP concentration (on the day after the third day of administration at 0.15, 0.3, or 0.5 mg/kg/day; only subjects from whom samples are available)
- Plasma drug concentration (on the day after the third day of administration at 0.15, 0.3, or 0.5 mg/kg/day): Assessment after breakfast is allowed if it is conducted prior to tolvaptan administration.

The investigator or subinvestigator will instruct the subject to completely discharge the urine immediately after breakfast, and start urine collection and fluid intake measurement to assess the following items.

- Daily urine volume
- Daily fluid intake
- Daily fluid balance
- Urine sodium excretion
- Urine potassium excretion
- Urine osmolality

2) Tolvaptan administration

The investigator or subinvestigator will instruct the subject to take tolvaptan with water after breakfast according to [Section 3.2](#).

3) At a feasible time

- Vital signs
- 12-lead ECG (on the day after the third day of administration at 0.15, 0.3, or 0.5 mg/kg/day)
- Edematous symptoms (after tolvaptan administration)
- Chest x-ray (on the day after the third day of administration at 0.15, 0.3, or 0.5 mg/kg/day)
- Concomitant drugs and therapies

- IMP compliance
- Adverse events

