3.7.4 Pharmacokinetic/Pharmacodynamic Assessments

3.7.4.1 Pharmacokinetic Assessments

3.7.4.1.1 Pharmacokinetic Blood Samples

- 1) Time points of blood sampling (see [Section 3.7.1.5](#) for time points in treatment at reduced dose)

Before administration, and 2 to 4, 10 to 14, and approximately 24 hours after administration on the third day of treatment with tolvaptan at 0.05, 0.15, 0.3, or 0.5 mg/kg/day.

- 2) Procedures for blood sampling and measurement

At time points shown in [Section 3.7.4.1.1 1](#)) and Table 3.7-1, a pharmacokinetic blood sample will be collected in a blood-collecting tube containing heparin sodium through an indwelling catheter or direct venipuncture. Cases where the subject cannot provide a blood sample for some reason will not be regarded as a deviation. The status (collected/not collected), and exact date and time of collecting a pharmacokinetic blood sample will be recorded in a CRF.

All samples will be shipped to the bioanalytical laboratory shown in Appendix 1 to determine the plasma concentrations of OPC-41061 (tolvaptan), DM-4103, and DM-4107 according to an established procedure. Detailed handling and shipping instructions are provided in Appendix 1.

- 3) Rationale for the time points of blood sampling

To determine the pharmacokinetics of tolvaptan in pediatric heart failure patients, data on the plasma concentrations of OPC-41061 and its metabolites (DM-4103 and DM-4107) will be collected. For the time points of blood sampling, a trial in adult CHF patients (Trial 156-06-004) was referred to. As a result of consideration, a total of 4 time points (before administration, at around peak time [2-4 hours after

administration], and at times in an elimination phase [10-14 hours and 24 hours after administration]) are set so that the pharmacokinetic parameters of OPC-41061 can be determined by population pharmacokinetic analysis which will be separately conducted.

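### SAP 10 takes the dose label from the sampling date, but the 24-hour plasma sample belongs to the previous day's dose

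*SAP*

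**What the plan says.** SAP 10 summarises tolvaptan and two metabolites by compound, time point and dose, and again by age group. The dose class comes from the sampling day: "The doses used for tabulation (0.05, 0.15, 0.3, and 0.5 mg/kg/day) will be those on the date of blood sampling". A parenthesis adds that this is the dose class recorded on the CRF.

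Protocol 3.7.4.1.1 sets four samples around the third dose at a step: "Before administration, and 2 to 4, 10 to 14, and approximately 24 hours after administration on the third day of treatment with tolvaptan". It describes the last two as "at times in an elimination phase [10-14 hours and 24 hours after" the dose. Where the fourth sample falls depends on what happens next:

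- **Stop after three days** (Protocol 3.7.1.3.10, which applies "If administration at the dose decided for each individual subject is completed in 3 days"). The sample is listed for the day after the last dose: "Plasma drug concentration: Assessment after breakfast is allowed". Protocol 3.7.1.5.5 does the same for a child who stops after three days at a reduced dose.
- **Extension at the same dose** (Protocol 3.7.1.4.1). It is taken on the fourth day, before dosing.
- **Reduction after the third day** (Protocol 3.7.1.5.1). It is taken on the first day at the lower dose, before that dose: "Plasma drug concentration (on the day after the third day of administration at 0.15, 0.3, or 0.5 mg/kg/day").

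Protocol 6.1 asks for summaries by time point and dose per kilogram and has no date rule. In SAP Appendix 1, the titles of PKT-1.1 to PKT-2.3 cover both the third day at each dose and the day after the last dose.

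**The concern.** A concentration should be tabulated under the dose that produced it. For three of the four samples the sampling date and the dosing date coincide. For the fourth they do not, and the date rule then gives either the wrong dose class or none.

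Pharmacokinetics is the secondary objective, and these by-dose and by-age tables are the pharmacokinetic output that this SAP specifies. The cells are small: 60 children over 4 doses and 3 age groups average 60 / 12 = 5 per cell if spread evenly (an assumption; the actual split is not given). In a cell of that size a single mislabelled value is visible in the mean and the coefficient of variation.

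**Working it through.** The documents give no figure to reproduce on this point. The check applies the SAP 10 rule to the 24-hour sample in each pathway and compares the label with the last dose before the draw.

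**Inputs.** Steps of 0.05, 0.15, 0.3 and 0.5 mg/kg/day (Protocol 3.2.2); reduction by one step only (3.2.3); sampling times (3.7.4.1.1); day schedules (3.7.1.3 to 3.7.1.5); daily cap of 15 mg (3.2.1). Let *d* be the dose given on the third day.

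| What follows the third day at *d* | Day of the 24-hour draw | Dose on that date | Last dose before the draw | Label under SAP 10 |
|---|---|---|---|---|
| Stops (3.7.1.3.10, 3.7.1.5.5) | Day after last dose | None | *d* | Undefined |
| Continues at *d* (3.7.1.4.1, 3.7.1.5.4) | Fourth day, before dosing | *d* | *d* | Correct |
| Reduced that morning (3.7.1.5.1) | First lower-dose day, before dosing | Next lower step | *d* | Wrong |

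The pre-dose, 2 to 4 hour and 10 to 14 hour samples are taken on the third day itself. The dose is *d* on that day and on the day before, so their labels are correct in every pathway.

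**Size of the mislabelling.** Ratio = dose that produced the sample / dose on the label:

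- 0.15 filed as 0.05: 0.15 / 0.05 = 3.0
- 0.3 filed as 0.15: 0.3 / 0.15 = 2.0
- 0.5 filed as 0.3: 0.5 / 0.3 = 1.67

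These are nominal ratios. The cap binds at 0.5 mg/kg/day above 15 / 0.5 = 30 kg and at 0.3 mg/kg/day above 15 / 0.3 = 50 kg. From 30 to 50 kg the last ratio, in milligrams, falls from 15 / 9 = 1.67 to 15 / 15 = 1.0.

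**Consistency with the rest of the plan.** SAP 5.7 gives a child reduced after three full days the dose before reduction as evaluation dose. SAP 6.1 credits the next morning's body weight to that dose. A plasma sample drawn before dosing that same morning would go under the lower dose by SAP 10.

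**After the fix.** With the label set to the last dose before the draw, all three rows of the table give *d*.

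**The case against.** The strongest reply is that the rule points to a dose class recorded on the CRF and need not be a calendar lookup. The CRF is not among the documents, so a dose field on the sampling page cannot be ruled out. But Protocol 3.7.4.1.1 lists only status, date and time for the sample, while 3.2.1 records dose with each administration. SAP 8.3 uses nearly the same phrase for the nominal dose category. The phrase says which kind of dose value to use, not which day's, so it does not clearly rescue the rule.

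Other parts of the reply stand:

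- A reader might infer that samples from three-day completers are lost. The PKT titles name the day after the last dose, and an analyst would naturally use the dose just finished. The SAP only fails to say so.
- A reader might infer that the lower-dose means will be raised. This is not shown. The misfiled sample falls on the first day at the reduced dose, which by the PKT titles is neither a third day nor the day after the last dose, so it may not enter that row.
- A reader might infer that reduced children have the highest concentrations. Nothing in the documents supports this, and Protocol 3.2.3 also allows reduction for safety concerns in general.
- The wrong label arises only when the reduction comes on the day after a full third day. A child extended first and reduced later already has a correctly labelled 24-hour sample.
- Protocol 3.7.4.1.1 says that the times were chosen for a separate population analysis. The PKT tables show individual values, and sampling times and compliance are listed (PDATA-7, SMED-1), so an error could be traced.

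**Conclusion.** Wrong as written, with minor severity. The date rule gives a wrong dose class to the 24-hour sample of children reduced on the day after a full third day at 0.15, 0.3 or 0.5 mg/kg/day. Their nominal dose is 3.0, 2.0 or 1.67 times the label before the cap. For children who stop after three days the rule gives no class. That pathway is the basic schedule, but the gap is one of wording.

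The conclusion rests on a literal reading of SAP 10 and on the CRF not carrying the preceding dose forward, which cannot be checked. The number of children reduced at that point is not given and may be small. The ratios compare doses and do not estimate bias in any tabulated mean. The effect stops at the descriptive by-dose tables and any figure that plots the 24-hour sample. The primary endpoint, the sample size and the population pharmacokinetic analysis do not depend on it.

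**What to change.** Replace the date rule in SAP 10 with: *The dose class used for tabulation is that of the last IMP administration before the sample; for the 24-hour sample this is the third-day dose.* Apply it to PKT-1.1 to PKT-2.3 and to any figure that plots the 24-hour sample. In the same edit, state whether the 24-hour samples of extended and reduced children enter these tables, since the titles leave this open.

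The cost is one sentence in the SAP and one derivation line. The dosing and sampling times are already collected (Protocol 3.2.1 and 3.7.4.1.1). No new data are needed and no dosing rule changes.

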## 11 Pharmacodynamic Analyses

A pharmacodynamic analysis will be performed in the pharmacodynamic analysis set.

For urine osmolality, daily urine sodium excretion, and daily urine potassium excretion, the data of the daily volume of the complete urine collection will be used.

As a subgroup analysis, the items will also be analyzed for each age group (young age, 6 months to less than 2 years; middle age, 2 years to less than 7 years; and old age, 7 years to less than 15 years).

The same analysis will be performed for each evaluation dose (0.05, 0.15, 0.3, and 0.5 mg/kg/day) (in the entire and each age group).

For the items listed below, descriptive statistics of measured values and changes from baseline at each time point after start of administration at evaluation dose will be determined.

An analysis will also be performed using data collected immediately before start of administration at evaluation dose as a baseline. In addition, data will be summarized by the number of days elapsed since start of administration.

- Daily fluid intake
- Daily fluid balance
- Serum osmolality
- Serum or blood sodium concentration
- Serum or blood potassium concentration
- Urine osmolality
- Daily urine sodium excretion
- Daily urine potassium excretion

For the plasma AVP concentration, descriptive statistics of measured values and changes from baseline will be calculated on the day after the final administration (CRF Visit).

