3.7.2.2 Daily Urine Volume

During the pretreatment observation period, daily urine volume will be measured for the time interval starting at urination (an instruction to urinate) after breakfast and ending at complete urination immediately before administration on the following day. After start of tolvaptan administration on the first day of the treatment period, daily urine volume will be determined for each time interval from the point after urination (an instruction to urinate) immediately before administration of the day to the point after urination (an instruction to urinate) immediately before administration on the following day.

For diapered subjects whose urine volume is difficult to determine by urine collection, urine volume may be estimated from the difference in the weight of diaper between before and after use (the weight at 1 g should be converted to 1 mL). The procedure should be established with consideration of measurement time to minimize fluctuations. The method of urine volume measurement (urine collection, diaper, or both) should not be changed throughout the trial period.

The status (measured/not measured), start date and time, and completion date and time of measurement, as well as daily urinary volume will be recorded in a source document and a CRF.

3.7.2.3 Edematous Symptoms (Edema [Lower Limbs, Eyelids, etc], Dyspnea, Jugular Venous Distension, Respiration Rate at Rest, and Pulse Rate)

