## **8.2.3      Daily Urine Volume**

The data based on which the accurate daily volume is measured will be used.

Descriptive statistics of measured values and changes from baseline will be calculated for each time point after start of administration at evaluation dose. An analysis will also be performed using data collected immediately before start of administration at evaluation dose as a baseline. In addition, data will be summarized by the number of days elapsed since start of administration.

The percent changes from baseline will also be summarized in the same manner.

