## 14 Changes in the Planned Analyses

- Since it was a clerical error, the following description in [Section 6.2](#) in the protocol was not to be performed: “In the subgroup analysis and the analysis by the evaluation dose, data collected on the day after the third day of administration at the evaluation dose, the day after the final administration at the evaluation dose, and the day after the final administration will be analyzed.” Since it was a clerical error, the following description for the plasma AVP concentration was added separately: “For the plasma AVP concentration, descriptive statistics of measured values and changes from baseline will be calculated on the day after the final administration (CRF Visit).”
- A summary of percent changes from baseline was added to the summary in [Section 7.5.2.3](#) in the protocol to consider the effect of baseline values.
- Since it was a clerical error, the summarization at each time point after the start of administration at the evaluation dose and the summarization by the number of days elapsed since the start of administration in [Section 7.7.4](#) in the protocol were not to be performed.
- Since it was considered difficult to assess several sites collectively, other edema in [Section 7.5.2.1](#) in the protocol was not to be summarized.
- For edema, dyspnea, jugular venous distention, respiration rate at rest, and pulse rate among the items of edematous symptoms, the schedule for assessment was when possible after the IMP administration on each date of assessment, and the assessment on the day after extended treatment would not be that on the third day of administration at the evaluation dose. Therefore, the assessment “on the day after the third day of administration at the evaluation dose, the day after the final administration at the evaluation dose, and the day after the final administration” in each section of [Section 7.5.2.2](#) in the protocol was regarded as that “on the third day of administration at the evaluation dose, the day of the final administration at

the evaluation dose, and the day of the final administration.” In accordance with this, [Section 7.3](#) in the protocol was also corrected to the corresponding description.

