- PDT-1.1.2 Descriptive Statistics for Daily Fluid Intake, Daily Fluid Balance, Urine Osmolality, Daily Urine Excretion of Sodium and Potassium by Age Category (Pharmacodynamics Analysis Set)
- PDT-1.1.3 Descriptive Statistics for Daily Fluid Intake, Daily Fluid Balance, Urine Osmolality, Daily Urine Excretion of Sodium and Potassium by Evaluation Dose (Pharmacodynamics Analysis Set)
- PDT-1.1.4 Descriptive Statistics for Daily Fluid Intake, Daily Fluid Balance, Urine Osmolality, Daily Urine Excretion of Sodium and Potassium by Evaluation Dose by Age Category (Pharmacodynamics Analysis Set)
- PDT-1.2.1 Descriptive Statistics for Daily Fluid Intake, Daily Fluid Balance, Urine Osmolality, Daily Urine Excretion of Sodium and Potassium with Day of Just Before Start of Evaluation Dose as Baseline (Pharmacodynamics Analysis Set)
- PDT-1.2.2 Descriptive Statistics for Daily Fluid Intake, Daily Fluid Balance, Urine Osmolality, Daily Urine Excretion of Sodium and Potassium with Day of Just Before Start of Evaluation Dose as Baseline by Age Category (Pharmacodynamics Analysis Set)
- PDT-1.2.3 Descriptive Statistics for Daily Fluid Intake, Daily Fluid Balance, Urine Osmolality, Daily Urine Excretion of Sodium and Potassium with Day of Just Before Start of Evaluation Dose as Baseline by Evaluation Dose (Pharmacodynamics Analysis Set)
- PDT-1.2.4 Descriptive Statistics for Daily Fluid Intake, Daily Fluid Balance, Urine Osmolality, Daily Urine Excretion of Sodium and Potassium with Day of Just Before Start of Evaluation Dose as Baseline by Evaluation Dose by Age Category (Pharmacodynamics Analysis Set)
- PDT-1.3.1 Descriptive Statistics for Daily Fluid Intake, Daily Fluid Balance, Urine Osmolality, Daily Urine Excretion of Sodium and Potassium by Days after the start of IMP administration (Pharmacodynamics Analysis Set)

- PDT-1.3.2 Descriptive Statistics for Daily Fluid Intake, Daily Fluid Balance, Urine Osmolality, Daily Urine Excretion of Sodium and Potassium by Days after the start of IMP administration by Age Category (Pharmacodynamics Analysis Set)
- PDT-1.3.3 Descriptive Statistics for Daily Fluid Intake, Daily Fluid Balance, Urine Osmolality, Daily Urine Excretion of Sodium and Potassium by Days after the start of IMP administration by Evaluation Dose (Pharmacodynamics Analysis Set)

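### Fluid intake, fluid balance and urine sodium and potassium excretion have no size-relative summary, so their pooled and by-dose results are confounded by body size

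*SAP*

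**What the plan says.** SAP 11 specifies "descriptive statistics of measured values and changes from baseline at each time point after start of administration at evaluation dose". The items include daily fluid intake, daily fluid balance, and daily urine sodium and potassium excretion. Protocol 6.2 takes the same approach. Balance is intake minus urine volume (Protocol 3.7.4.2.2). Excretion is urinary concentration times daily volume (Protocol 3.7.4.2.7 and 3.7.4.2.8). None of these is divided by weight, and no table in the PDT-1 series of SAP Appendix 1 names a scaled version.

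The results are pooled over all ages and also broken down. SAP 11 states: "As a subgroup analysis, the items will also be analyzed for each age group". It repeats the analysis for each evaluation dose "in the entire and each age group". PDT-1.1.4, 1.2.4 and 1.3.4 are the dose-within-age tables.

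Urine volume is treated differently. SAP 8.2.3 plans absolute values and changes, and then adds: "The percent changes from baseline will also be summarized in the same manner". SAP 14 records the reason for the addition, which is to allow for baseline level. CT-6.7.4 to CT-6.7.6 carry it overall, by age, by dose, and by dose within age.

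**The concern.** Across this age range body weight varies several-fold, and a daily amount of fluid or electrolyte rises with it. A pooled mean in mL or mEq therefore leans towards the heavier children.

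The by-dose rows are the more exposed part. Evaluation dose is not randomised: each child reaches it by titration on the child's own urine response (Protocol 3.2.2 and 7.4), so nothing balances age or weight across dose rows. If one row holds older children, its absolute intake, balance and excretion will be larger even when the response per kg is the same. In a trial meant to define a dose, that could be read as a dose pattern.

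The plan uses relative scales elsewhere: dose in mg/kg, the titration trigger as 150% of the child's own baseline, the primary endpoint as percent weight change, and percent change for urine volume. Only these four items lack one. Percent change would not suit fluid balance, which is a difference that can lie near zero or change sign. A per-kg scale would.

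**Working it through.** The plan states no figure for these items, so there is none to reproduce. The documents also give no weights and no spread for the four measures. Both are assumptions below, shown as ranges.

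**1. Contrast between dose rows.** Suppose the per-kg response is identical. The ratio of two rows' mean amounts is then the ratio of their mean weights. Assumed mean weights are 8, 14 and 28 kg (young, middle, old).

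| Imbalance | Row A mix (young/middle/old) | Row B mix | Mean weights | Ratio |
|---|---|---|---|---|
| Mild | 30/40/30% | 15/40/45% | 16.4 and 19.4 kg | 1.18 |
| Strong | 50/40/10% | 10/40/50% | 12.4 and 20.4 kg | 1.65 |

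For example, 0.5×8 + 0.4×14 + 0.1×28 = 12.4 and 0.1×8 + 0.4×14 + 0.5×28 = 20.4; 20.4/12.4 = 1.65.

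**2. Who drives the pooled mean.** Protocol 3.3.1 caps the old and middle groups at 24 each. If 60 children are treated and both caps fill, 12 are in the young group. Total weight is 12×8 + 24×14 + 24×28 = 96 + 336 + 672 = 1104 kg. The old group is 40% of subjects and 672/1104 = 61% of the total. The young group is 20% of subjects and 96/1104 = 9%.

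**3. How much of the spread is weight.** The model is amount = weight^a × per-kg amount, with a = 1 or 0.75 and a per-kg coefficient of variation (CV) of 0.3, 0.5 or 0.7. Weight is log-uniform within each age group. The three weight scenarios run from 7–11, 11–20 and 20–45 kg (narrow) to 5–12, 8–25 and 14–60 kg (wide). The share due to weight is Var(weight^a)/Var(amount).

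- Measured values, all ages pooled: 21% to 77%. The share passes 50% in 7 of 18 settings: all six with CV 0.3 and one with CV 0.5.
- Measured values within one age group: 2% to 62%.
- Absolute changes from baseline (a = 1, baseline per-kg CV about 0.4, mean relative change 0 to 50%, SD 30% to 50%): 0% to 34%. This models a positive amount such as intake or excretion. Fluid balance was not modelled.
- The heaviest third of children carries 54% to 58% of total body weight.

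**4. Cell size in the dose-within-age tables.** Four doses × three age groups = 12 cells; 60/12 = 5 children on average.

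**5. What per-kg scaling leaves behind.** With a = 1, nothing. With a = 0.75, the per-kg amount still varies as weight^(−0.25). In the middle weight scenario (6–11, 9–22, 16–50 kg) the variance of log weight is about 0.303, so the residual is 0.25² × 0.303 = 0.0189. The log-scale variance of the per-kg amount is ln(1 + CV²), which is 0.0862 at CV 0.3 and 0.399 at CV 0.7. The residual share is 0.0189/0.1051 = 18% at CV 0.3 and 0.0189/0.418 = 4.5% at CV 0.7.

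**The case against.** The strongest reply is that the plan already stratifies. The dose-within-age tables act directly on the age mix that produces the ratios in step 1. That is true, and it is the main reason the point is modest. What remains is weight spread inside a group and cells of about five children. Protocol 3.3.1 itself foresees such spread, with a rule for children who weigh less than half the ideal weight at their group's lower age limit.

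The ratios also assume equal per-kg response, so they show how large an artefact could be and do not estimate one. That stands. Per-kg scaling is not perfect either: step 5 shows a possible residual, and the 15 mg/day ceiling means dosing is not strictly per kg (at 0.5 mg/kg/day it binds above 15/0.5 = 30 kg). Nor would scaling turn rows formed by titration on response into a clean dose comparison. These are reasons to add a per-kg scale and not to replace the absolute one.

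The stakes are limited. Of nine pharmacodynamic items, five are concentrations or osmolalities that do not scale with size. Medians, ranges and individual listings are also planned.

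A reader might infer two further faults that the documents do not support. The first is that urine volume has the same gap. It does not, because percent change is planned in every breakdown. The second is that collections should be rescaled to 24 hours, because the protocol records "start date and time, and completion date and time of measurement" and the SAP states no use for them. On treatment days each interval runs from one predose void to the next under once-daily dosing, and intake is measured over the same interval. SAP 8.2.3 already limits urine volume to accurately measured days, and SAP 11 limits electrolyte excretion to complete collections. Rescaling is not required.

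**Conclusion.** The point holds for four items: daily fluid intake, fluid balance, and urine sodium and potassium excretion. They are reported only in absolute units, so their pooled and by-dose summaries are confounded by body size. Under the assumed weights, age mix alone could separate two dose rows by about 1.2- to 1.65-fold.

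A reader might go further and say that these results mostly reflect body size. The documents do not show that. For measured values it is possible under some assumptions, mainly when per-kg variation is low. For changes from baseline, which are closer to a treatment effect, weight accounted for at most 34% of the variance in any setting examined. A stated loss of effective sample size would not be secure either, because it requires assuming a common per-kg effect and a weight distribution that the documents do not give.

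The analyses are descriptive and secondary. The primary endpoint combines percent weight change with a within-child urine volume comparison and is not affected. This is a cheap improvement, not a defect in the trial's main conclusion.

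**What to change.** In SAP 11 and the PDT-1 tables, add per-kg summaries of the four items: mL/kg/day for intake and balance, mEq/kg/day for sodium and potassium. Divide by the Day 1 predose weight, which SAP Table 3.4-1 already defines as the weight baseline, so that weight loss on treatment does not alter the denominator. Present them overall, by age group and by evaluation dose, and keep the absolute tables alongside. Urine volume needs no change.

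The cost is SAP wording, one derived variable per item and extra tables. No new data are needed, because weight is measured throughout. The limitation to state is the possible small residual size effect if amounts do not rise in proportion to weight.
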